10.3.4 Reporting of SAE

SAE Reporting to Sponsor

- The primary mechanism for reporting an SAE to the Sponsor will be the electronic data collection tool.
- If the electronic system is unavailable, then the site will use the SAE paper CRF in order to
 report the event within 24 hours. Notification by email with scanned copy of the SAE paper
 CRF or facsimile transmission of the SAE paper CRF to the SAE coordinator is acceptable.
- The site will enter the SAE data into the electronic system as soon as it becomes available.
- The Investigator and the Sponsor (or Sponsor's designated agent) will review each SAE report and the Sponsor (or Sponsor's designated agent) will evaluate the seriousness and the causal relationship of the event to study intervention. In addition, the Sponsor (or Sponsor's designated agent) will evaluate the expectedness according to the reference document (Investigator Brochure or Summary of Product Characteristics). Based on the Investigator and Sponsor's assessment of the event, a decision will be made concerning the need for further action.
- After the study is completed at a given site, the electronic data collection tool will be taken
 off-line to prevent the entry of new data or changes to existing data.

Version 6.0 87 of 138 April 11, 2024

If a site receives a report of a new SAE from a study subject or receives updated data on a
previously reported SAE after the electronic data collection tool has been taken off-line, then
the site can report this information on a paper SAE form or to the SAE coordinator by email
or fax.

Suspected Unexpected Serious Adverse Reactions (SUSARs)

Any AE that is serious, associated with the use of the IMP, and unexpected (SUSAR) has additional reporting requirements, as described below.

- If the SUSAR is fatal or life-threatening, associated with IMP, and unexpected, regulatory
 authorities and IECs will be notified within seven calendar days after the Sponsor learns of
 the event. Then followed by as complete a report as possible within 8 additional calendar
 days.
- If the SUSAR is not fatal or life-threatening but is otherwise serious, associated with the IMP, and unexpected, regulatory authorities and IECs will be notified within 15 calendar days after the Sponsor learns of the event.

The Sponsor (or Sponsor's designated agent) will notify the Investigators in a timely fashion of relevant information about SUSARs that could adversely affect the safety of subjects. Follow-up information may be submitted if necessary.

The Sponsor (or Sponsor's designated agent) will also provide annual safety updates to the regulatory authorities and IECs responsible for the study. These updates will include information on SUSARs and other relevant safety findings.

The minimum information required for an initial report is:

- Name of person sending the report (e.g., name, address of Investigator);
- Subject identification (screening/randomization number, initials, NOT subject name);
- Protocol number;
- Description of SAE;
- Causality assessment, if possible.

After receipt of the initial report, the Sponsor (or Sponsor's designated agent) will review the information and, if necessary, contact the Investigator, to obtain further information for

Version 6.0 88 of 138 April 11, 2024

assessment of the event. The Sponsor (or Sponsor's designated agent) will be responsible for all information processing and reporting according to local legal requirements. Where necessary, Investigators will inform regulatory authorities in their own countries.

Version 6.0 89 of 138 April 11, 2024

10.4 Appendix 4: Contraceptive Guidance

Woman of Childbearing Potential (WOCBP)

A woman is considered fertile following menarche and until becoming post-menopausal, unless permanently sterile. All subjects in this study are WOCBP and must follow the contraception requirements below. This includes women with tubal infertility from endometriosis.

Exception: Women who have had a documented bilateral salpingectomy or bilateral tubal ligation may participate in the study, but do not have to follow protocol-specified contraception requirements.

Note: Documentation of bilateral salpingectomy can come from the site personnel's review of the subject's medical records, medical examination, or medical history interview.

Contraception Requirements

A woman is eligible to participate in the study if she meets one of the following criteria:

• Is heterosexually abstinent;

Note: Sexual abstinence is defined as refraining from heterosexual intercourse during the entire period of risk associated with the study intervention. The reliability of sexual abstinence needs to be evaluated in relation to the duration of the study and the preferred and usual lifestyle of the subject.

OR

- Is heterosexually active and agrees to use two forms of the following contraception methods consistently and correctly during the protocol-defined time frame in inclusion and exclusion criteria:
 - Condoms used with spermicide (cream, spray, foam, gel, suppository, or polymer film)
 or Phexxi
 - o Diaphragm used with spermicide (condom may or may not be used) or Phexxi
 - o Cervical cap used with spermicide (condom may or may not be used) or Phexxi
 - o Vaginal sponge impregnated with spermicide or Phexxi; used with a condom

Note: Hormonal contraception except for sporadic use of emergency contraception is not permitted during the study. Male and female condoms should not be used at the same time. **OR**

• Has undergone bilateral tubal sterilization or bilateral salpingectomy;

OR

• Has a vasectomized partner.

Note: Partner must be the sole male sexual partner of the WOCBP and the absence of sperm has been confirmed. If not, a two-forms method of contraception must be used.

Subjects should avoid pregnancy from signing the consent until the completion of the study or 3 months after the last dose of IMP, whichever is longer.

Pregnancy Testing: Study subjects should only be included after a negative serum pregnancy test at Visit 1 and a negative urine pregnancy at Visit 3. Urine pregnancy testing to be done at Visit 3, 5, 7, 9 and 10 through home pregnancy test kit. It will be under the supervision of investigators and the results will be recorded in source documents, then collected in EDC.

Version 6.0 91 of 138 April 11, 2024

10.5 Appendix 5: Washout Intervals

Therapy	Minimum Interval for Washout*
Hormonal/Anti-Hormonal Therapy	
Medroxyprogesterone Acetate (Depo-Provera®)	10 months prior to Visit 1
GnRH Agonist − 3 months depot (Lupron®, Zoladex®)	6 months prior to Visit 1
Injectable hormonal contraception with 3-month duration	6 months prior to Visit 1
Injectable hormonal contraception with 2-month duration	4 months prior to Visit 1
Injectable hormonal contraception with 1-month duration	2 months prior to Visit 1
GnRH Agonist (including 1 month depot)	
GnRH antagonist	
Selective Progesterone Receptor Modulators (e.g., Ulipristal	
acetate)	2
Nafarelin acetate (Synarel [®])	3 months prior to Visit 1
Danazol (Cyclomen®)	
Aromatase inhibitors	
Menotropins and human chorionic gonadotropin (hCG)	
Oral Contraceptives**	
Oral, transdermal or intravaginal Estrogen Preparations	1 months prior to Visit 1
Oral, intravaginal or transdermal progesterone/progestin	1 months prior to visit 1
Preparations (except Levonorgestrel 1.5 mg)	
Hormonal and Non-Hormonal IUD, sub-dermal progestin	
implant (e.g., Nexplanon®)	Removal at least 1 month
NuvaRing®	prior to Visit 1
Analgesics	
Non-steroidal anti-inflammatory drugs (NSAIDs) (e.g.	
aspirin)	1 day prior to Visit 2
COX-2 inhibitors	
Other non-specified analgesics (e.g. acetaminophen or	
paracetamol)	
Opioid analgesics (e.g. tramadol and tapentadol)	5 days prior to Visit 1, no
	more than 14 days of
	continuous use within 6
	months
Medications that affect PRL level	

Therapy	Minimum Interval for Washout*
Antipsychotics and antidepressants: Sulpiride, Risperidone,	
Haloperidol, Clomipramine, Phenothiazines, Nomifensine,	
etc.	
Antiepileptic or anticonvulsant: Diazepam, Phenytoin	1 months prior to Visit 1
Sodium, Phenobarbital, etc.	
Injection use of Histamine H1/H2 receptor antagonists:	
Promethazine, Famotidine, etc.	
Other medications that affect PRL level: Bromocriptine,	
Cabergoline, Lergotrile, Lisuride, Metergoline, Quinagolide,	
Terguride, Isoniazide, Domperidone, Metoclopramide,	
Methyldopa, Reserpine, etc.	
Others	
Herbal remedies containing Hypericum perforatum (e.g. Kava	At Visit 1
kava and St. John's wort)	
Cannabinoids	1month prior to Visit 1
Growth hormone replacement	
Anti-tumor necrosis factor (TNF)/anti-nerve growth factor	2 months prior to Visit 1
(NGF)	

[figure not shown]
^{*} This is the minimum washout; however, subjects may not enter Screening until return to one normal menstrual cycle.

If the type of medications and the length of Washout are not listed in the table above, consult the Hope Medicine Medical Monitor for a recommendation.

Note: The drugs above should not be withdrawn by the investigator if used for treatment purposes, but rather the washout period may be used if the prescriber recommends discontinuation of any of these drugs.

^{**} Subjects must complete the mandatory month of washout from oral contraceptives and subsequently have a menses/period. Bleeding due to withdrawal of the oral contraceptives cannot be considered the required menses/period.

10.6 Appendix 6: Numeric Pain Rating Scale (NRS)

Version 6.0 94 of 138 April 11, 2024

10.7 Appendix 7: Patient Global Impression of Change (PGIC)

Since I started taking the IMP, my endometriosis related pain has:		
☐ Very much improved		
☐ Much improved		
☐ Minimally improved		
□ Not changed		
☐ Minimally worse		
☐ Much worse		
☐ Very much worse		

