Date	Screening Visit	Screening Visit 22	Week 1	Week 3 (Day 15 ±3)	Week 5 (Day 29 ±3)		Week 9 (Day 57 ±3)	Week 11 (Day 71 ±3)	Week 13 (Day 85 ±2/4)	Week 25
	Up to 14 days prior to V2	At least 35 days prior to V3	(Day 1) ³							(Day 169 ±7)
Visit (V)	V1	V2	V3	V4	V5	V6	V7	V8	V9	V10
PGIC			2		X		X	2	X	X
EHP-5			X		X		X		X	X
ADA sampling ²⁷			X	X	X		X		X	X
PK sampling ²⁸			X	X	X		X	X	X	X

Abbreviation: ADA = anti-drug antibody; AE = adverse event; anti-HAV = hepatitis A virus antibody; anti-HIV = human immunodeficiency virus antibodies; ASCUS = atypical squamous cells of undetermined significance; BMI = body mass index; BSAP = bone specific alkaline phosphatase; CA-125 = cancer antigen-125; CPSSS= Composite pelvic signs and symptoms score; CTX = C-terminal telopeptide of type 1 collagen; DXA = dual energy X-ray absorptiometry; DHEAS = Dehydroepiandrosterone-sulfate; ECG = electrocardiogram; e-Diary: Electronic Diary, EHP-5 = Endometriosis Health Profile-5; EOT = end of treatment; FSH = follicle-stimulating hormone; FT3= Free triiodothyronine; FT4= Free thyroxine; eGFR = estimated glomerular filtration rate; GH=growth hormone; HBsAg = hepatitis B virus surface antigen; HBcAb = Hepatitis B core antibody; HCV = hepatitis C virus; LH = luteinizing hormone; IMP = investigational medicinal product; MRI = magnetic resonance imaging; P1NP = procollagen type 1N-terminal propertied; PGIC = Patient Global Impression of Change; PK = Pharmacokinetics; PRL = Prolactin; PVC = Premature ventricular contractions; Q2W = once every 2 weeks; QTcF = QT interval corrected for heart rate using Fridericia's correction formula; RNA = ribonucleic acid; V = Visit; TSH = thyroid stimulating hormone; TVU = transvaginal ultrasound.

- The time interval between Screening Visit 1 and Screening Visit 2 is no longer than 14 days. Specific procedures listed for Visit 1 could be scheduled during this period.
- 2. At Screening Visit 2, e-Diary will be dispensed. The time interval between Visit 2 and Visit 3 will at least cover a 35-day baseline period.
- 3. Day 1 should start from the menses cycle days 1 to 5. Data obtained from Day 1 will be utilized as baseline for analysis (except for e-Diary data).
- 4. The EOT Visit should be 14 days from the last dose of IMP (Visit 8). The time window of EOT visit is dependent on the schedule of the PK subgroup (intensive PK, ±2 days, sparse PK, ±4 days). The arrangement for TVU, pelvic examination or lab tests could be based on menses cycle.

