5.1 Inclusion Criteria

Subjects are eligible to be included in the study only if all of the following criteria apply:

- 1. Pre-menopausal female subjects, between 18 and 49 years of age, inclusive, at the time of signing informed consent.
- 2. Subject must have a clinical diagnosis of endometriosis (laparoscopy or laparotomy) as documented by medical records within 10 years before screening.
- 3. Subject must have a Composite Pelvic Signs and Symptoms Score (CPSSS, refer to Section 8.11 and 10.9) total score of ≥ 6 at screening with a score of at least 2 for DYS and at least 2 for NMPP.
- 4. Subject must have reported at Baseline at least 2 days of "moderate" or "severe" pain for DYS and NMPP, with NRS score of at least 4 (where 0 represents absence of pain and 10 indicates unbearable pain, refer to Section 8.1.3 and 10.6).
- 5. Mammography or contrast-enhanced breast MRI performed within the last 12 months prior to randomization without clinically significant abnormal findings in subjects aged 40 and over only (subject with BI-RADS Classification 1 3 is eligible for randomization).
- 6. Subject must have at least two consecutive regular menstrual cycle (i.e. 21 to 35 days in duration) prior to Day 1.
- 7. Subject agrees to use required (nonhormonal) birth control methods during the entire length of participation in the study (refer to Section 10.4) and agrees to avoid pregnancy from signing the informed consent until 3 months after the last dose.
- 8. Subject must agree to use only those rescue analgesics (i.e. not prophylaxis) permitted by the protocol during the Screening, Treatment and Posttreatment follow-up Periods for her endometriosis-associated pain. (refer to Section 6.5.1).

Version 6.0 33 of 138 April 11, 2024

- 9. In the Investigator's opinion, subject is able to understand the nature of the study and any risk involved in participation in this study and is willing to cooperate and comply with the protocol restrictions and requirements, including transvaginal ultrasound (TVU).
- 10. Subject agrees not to participate in another interventional study while participating in the present study.
- 11. Subject who is willing to limit alcohol consumption during the study to no more than approximately one alcoholic drink or equivalent [beer (354 mL/12 ounces), wine (118 mL/4 ounces), or distilled spirits (29.5 mL/1 ounce)] per day.

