9.4.4 Primary Efficacy Endpoints

The primary efficacy endpoint is the mean change of DYS measured by NRS from Baseline to Week 12.

Measurement of Baseline: The baseline measurements will be derived from the last *complete* menstruation cycle during the Screening Period prior to Day 1.It will be designated as the baseline menstrual cycle and is defined as the interval from the first day of the menstruation to the day before the first day of the next menstruation.

Measurement of Week 12: Because the Week 12 (EOT) visit may or may not occur during menstruation, the measurement of Week 12 will be defined by the following 2 approaches, depending on the scenarios. The objective of these approaches is to capture a complete menstrual cycle and designate it as the EOT menstrual cycle.

- If EOT visit occurs during menstruation, the *EOT menstrual cycle* is defined as the interval that begins from the first day after the end of the previous menstruation to the last day of the menstruation during which the EOT visit occurred. It is expected that the end of this menstruation may be days after the EOT visit.
- If EOT visit occurs outside of a menstruation period, the closest menstruation period to the EOT visit will be identified. This menstrual period may be before or after the EOT visit. In either case, the *EOT menstrual cycle* will begin at the end of the menstruation

Version 6.0 64 of 138 April 11, 2024

period *immediately before* the closest menstruation period to the last day of the closest menstruation period.

The mean change will be summarized for each treatment group with point estimate and 95% CI and will be compared for each HMI-115 treatment group to the placebo group using analysis of covariance models (ANCOVA) with treatment, the randomization stratification factor of region as the fixed effects and baseline DYS as covariate. In addition, a mixed-effect model repeated measures (MMRM) method with treatment, the randomization stratification factor of region, and visit as the main effects, and treatment-by-visit interaction will be used as a sensitivity analysis.

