- The Week 12 measurement: Because the Week 12 (EOT) visit may or may not occur during menstruation, the measurement of Week 12 will be defined by the following 2 approaches, depending on the scenarios. The objective of these approaches is to capture a complete menstrual cycle (menstruation period should be ≥ 2 days) and designate it as the EOT menstrual cycle.

[figure not shown]
- If EOT visit occurs during menstruation, the EOT menstrual cycle is defined as the interval that begins from the first day after the end of the previous menstruation to the last day of the menstruation during which the EOT visit occurred. It is expected that the end of this menstruation may be days after the EOT visit.

- If EOT visit occurs outside of a menstruation period, the closest menstruation period to the EOT visit will be identified. This menstrual period may be before or after the EOT visit. In either case, the EOT menstrual cycle will begin at the end of the menstruation period immediately before the closest menstruation period to the last day of the closest menstruation period.

Or

The average score is calculated by adding up the daily DYS measured by NRS during analysis window and dividing by the actual number of days with non-missing daily DYS data.

The **primary estimand** is described by the following attributes:

Treatment conditions of interest:	HMI-115 at 60,120 and 240 mg vs. placebo. Placebo treatment is the control group.
Subject population:	Women with moderate to severe endometriosis-associated pain and have surgical diagnosis
Endpoint:	Mean change (change from baseline) in DYS measured by NRS at Week 12 measurement
Population-level summary:	Differences between each HMI-115 treatment group compared with placebo in mean change (change from baseline) in DYS measured by NRS at Week 12, including least square mean (LSM) with its associated standard error (SE) and 95% CIs by using ANCOVA
Intercurrent events (ICEs) and strategies to handle ICEs:	
Premature withdrawal from study treatment due to any reasons (Hypothetical strategy)
 
At least 15% increase in average pill count of rescue analgesic medications(endometriosis-associated) compared to Baseline. (Composite strategy)

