The threshold for reduction in pain will be determined based on a ROC analysis using the PGIC assessment at Week 13 as an anchor and mean change of DYS measured by NRS from Baseline to Week 12 as the independent variable. The PGIC is a 7-point response scale: "Since I started taking the IMP, my endometriosis related pain has: very much improved (1), much improved (2), minimally improved (3), not changed (4), minimally worse (5), much worse (6), very much worse (7)." **The responses of "very much improved (1)" and "much improved (2)" on PGIC will be used to define PGIC responders**, and the threshold for response will be chosen to balance sensitivity and specificity. The threshold with maximum Youden's index (Youden's index=sensitivity + specificity – 1) will be selected as optimal threshold. Treatment group will be considered in ROC analysis. No other covariates will be included in the ROC analysis.

Empirical Cumulative Distribution Function (eCDF) Curve

In addition to the anchor-based method, the eCDF method will be used to determine the clinically meaningful improvement. The eCDF curves display a continuous view of the mean score change (both positive and negative) in DYS at Week 12 on the horizontal axis, with the vertical axis representing the cumulative proportion of patients experiencing up to that level of score change. An eCDF curve should be plotted for each distinct anchor category and treatment group.

Dose-Response Relationship

To study the dose-response relationship, the mean CFB to Week 12 measurement will be plotted versus nominal and log-transformed dosage (placebo, HMI-115 60mg, 120mg and 240mg). The dosage (0, 60, 120, 240) will be log-transformed using the function $\log(\text{dosage}+1)$, where \log represents the natural logarithm function. A simple linear regression model will be fitted as a function of dose to characterize the dose-response relationship. In case of lack-of-fit

of the simple linear regression model, multivariate or non-linear regression models may be explored.

The following SAS code will be used:

```
PROC REG data=data;
```

```
  MODEL cfb = log_dose / clb;
```

```
RUN;
```

```
PROC REG data=data;
```

```
  MODEL cfb = dose / clb;
```

```
RUN;
```

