9.3 PGIC

The number and percentage of subjects in each PGIC response category (7-point scale) will be summarized at each visit including Week 5, Week 9, Week 13 and Week 25 for treatment group. The percentage of subjects with response of "Much Improved" or "Very Much Improved" will be combined and labeled as "Much Improved or Better". The remaining five categories of the PGIC scale will be combined and labeled "Other". The number and percentage of subjects with response of a) "Much Improved or Better" and b) "Other" will be summarized at each visit by treatment group, and comparison will be made between each HMI-115 treatment group and placebo group using a chi-square test, if the counts of equal or more than 20% cells are less than 5, the comparison will use Fisher exact test. In addition, the scores of PGIC will be summarized as continuous data to calculate means of each treatment group.

Score	Response category	Pooled category
1	Very much improved (better outcome)	Much Improved or Better (PGIC Responder)
2	Much improved	
3	Minimally improved	
4	No change	
5	Minimally worse	Other (PGIC Non-responder)
6	Much worse	
7	Very much worse (worse outcome)	

Statistical comparisons between each HMI-115 treatment group and placebo group in score (ranging 1 to 7) at each visit will be performed using ANOVA with treatment group and the randomization stratification factor of region as the fixed effects. If a subject has at least 15% increase of rescue medication use or changed to Opioids/Opioids+NSAIDs from NSAIDs at a particular visit (referring to Appendices Table 12.2) compared to baseline, such subjects will be considered as non-responders ('No change' category which the value will be set as 4) in the PGIC responder analysis for that visit.

PGIC data will be listed by subject and visit.

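### The DYS threshold is anchored on a PGIC answered at the Week 13 visit, yet for roughly one third to just over one half of women (depending on cycle length) the DYS score it is paired with comes from a menstruation that starts after that visit

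*Protocol*

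**What the plan says.** **Anchor.** The PGIC item is "Since I started taking the IMP, my endometriosis related pain has", followed by seven categories (Protocol 10.7). It is "summarized at each visit including Week 5, Week 9, Week 13 and Week 25" (SAP 9.3). Week 13 is the EOT visit, planned for Day 85 with a window of "intensive PK, ±2 days, sparse PK, ±4 days" (Protocol 1.3, SoA footnote 4).

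**Score.** The Week 12 DYS value is a mean of daily scores: "adding up the daily DYS measured by NRS during analysis window and dividing by the actual number of days with non-missing daily DYS data" (SAP 7.2.1). The window is the EOT menstrual cycle, which contains one menstruation.
- If the visit falls in a menstruation, that one is used to its last day: "It is expected that the end of this menstruation may be days after the EOT visit" (Protocol 9.4.4).
- Otherwise the closest one is used: "This menstrual period may be before or after the EOT visit" (SAP 7.2.1).

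**Pairing.** SAP 7.2.5 sets the threshold by ROC, "using the PGIC assessment at Week 13 as an anchor and mean change of DYS measured by NRS from Baseline to Week 12"; the DYS change is the predictor. It uses observed DYS values and takes the cut-off with the largest Youden index. The eCDF curves are drawn by anchor category and treatment group. Protocol 9.4.3 says the ROC and eCDF will define clinically meaningful improvement and the DYS responder.

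**The concern.** An anchor-based threshold assumes that the rating and the score describe the same experience. Here a woman can give her global rating before any of the DYS days that the rating is used to classify. A woman visited in mid-menstruation gives it before some of them.

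No time condition appears in SAP 7.2.5, and the sensitivity analysis in SAP 7.2.3 changes only the rescue-medication rule. The Week 24 rule (Protocol 9.4.5, SAP 7.3.1) looks only backward: it takes the latest menstruation before the EOS visit, or the preceding cycle if the visit falls in menses. So the Week 24 score never follows its visit, while the Week 12 score, the one used in the ROC, can.

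At stake is the quality of the threshold. Mistimed pairs misclassify women relative to the score, which lowers ROC accuracy and makes the Youden cut-off less stable.

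**Working it through.** The documents state no share of affected women, so there is no figure to reproduce. The share has to be derived.

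**Inputs from the documents.** Cycle length L: entry requires "at least two consecutive regular menstrual cycle (i.e. 21 to 35 days in duration) prior to Day 1" (Protocol 5.1). Day 1 falls on cycle days 1 to 5 (SoA footnote 3). The visit is on Day 85, that is, 84 days later. A menstruation must last at least 2 days (SAP 7.2.1).

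**Assumptions.** The distribution of L, the within-woman variation, and the menstruation length p (2 to 7 days in step 1, 5 in step 2, uniform on 3 to 7 in step 3). Closest is measured to the end of the previous menses or the start of the next.

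**Step 1: random phase.** The visit falls in menses with probability p/L, and the rest splits evenly:

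P(scored menses starts after visit) = (L − p)/(2L)

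- L = 28, p = 5: 23/56 = 41%
- L = 21, p = 7: 14/42 = 33%
- L = 35, p = 2: 33/70 = 47%

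**Step 2: phase fixed by the Day 1 rule.** With p = 5, no cycle variation and an exact Day 85 visit, the visit falls on cycle day c + (84 mod L), with c = 1 to 5.
- L = 28: 84 mod 28 = 0, cycle days 1–5, always in menses; after = 0%.
- L = 26: 84 mod 26 = 6, cycle days 7–11. The previous menses ended 2–6 days ago and the next is 16–20 days off; after = 0%.
- L = 29: 84 mod 29 = 26, cycle days 27–29 or days 1–2 of the next cycle; after = 3/5 = 60%.
- L = 30: 84 mod 30 = 24, cycle days 25–29. The next menses is 2–6 days off and the last ended 20–24 days ago; after = 100%.

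The share therefore depends strongly on cycle length.

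**Step 3: mixed populations by simulation** (L within 21–35, within-woman SD 0, 1.5 or 2.5 days, visit window 0 or ±4 days):

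| Cycle length | Scored menses starts after visit |
|---|---|
| N(27, 2.5) | 33–38% |
| N(28, 2) | 36–41% |
| N(28, 3) | 43–46% |
| N(29, 3) | 49–50% |
| Uniform 21–35 | 46–51% |
| N(30, 3) | 53–54% |

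Measuring closeness to the start of the previous menses instead adds about 4–9 points. Runs with menses of 4–6 days and a within-woman SD of 1.5 days gave a similar range of shares. In them, the scored menses began a median of 4–7 days after the visit (90th percentile 10–12).

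**Step 4: effect on the ROC (illustration).** 136 women, SD of change 2.0 (both from Protocol 9.2), with the between-cycle correlation and the mistimed share assumed:

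| Correlation | Mistimed | AUC aligned | AUC as planned | Loss |
|---|---|---|---|---|
| 0.5 | 40% | 0.836 | 0.766 | 0.070 |
| 0.7 | 40% | 0.835 | 0.794 | 0.041 |
| 0.85 | 30% | 0.836 | 0.820 | 0.016 |

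The SD of the cut-off rises from 0.48–0.49 to 0.50–0.57, an increase of about 0.01 to 0.09 NRS points.

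**Step 5: does alignment help?** A further simulation paired the PGIC with the last menses begun by its date, cut off at that date. AUC rose in every scenario: from 0.81–0.88 to 0.90–0.91 if the PGIC tracks the last menses, and from 0.77–0.88 to 0.82–0.89 if it tracks the treatment-period average. That run had no 2-day minimum.

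**The case against.** A reader might infer that the anchor cannot reflect the pain scored and that the threshold is invalid. The documents do not support that. The PGIC asks about all endometriosis-related pain since the start of IMP, so it covers earlier treated menstruations and non-menstrual pain. Change in DYS should also be correlated between adjacent cycles, and step 4 itself assumes 0.5 to 0.85. The anchor is weaker in a subset of women. That part of the objection stands.

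It also stands that the computed harm is modest, that no bias in the threshold has been quantified, and that the ROC and eCDF sit under other analyses. The SAP plans no test that uses the threshold, and Protocol 9.4.3 defines the responder only once results are available.

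The closest-cycle rule was chosen to capture a complete cycle. Looking backward has its own cost: for affected women the aligned menstruation ended a median of about 20 days before the PGIC and began about 24–25 days before it. Cutting off at the PGIC date also shortens the menses of women visited mid-period, about 23–24% in one run, and leaves about 5% of all women with a single scored day. This is a reason to require at least 2 recorded days and to show both cut-offs. It does not justify leaving the pairing unexamined, since alignment raised AUC even with the cut-off at the PGIC date.

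**Conclusion.** The timing mismatch is real and follows from the plan's own definitions. It affects about one third to just over one half of women in mixed populations. A reader might take a single figure such as nearly half as established, but it holds only for particular cycle-length distributions, and the documents give only the 21 to 35 day range. For affected women every scored DYS day post-dates the anchor.

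The consequence is a weaker anchor–score correlation and a modestly noisier Youden cut-off and eCDF by anchor category. The AUC losses of about 0.02 to 0.07 rest on an assumed anchor strength and between-cycle correlation. The primary ANCOVA, its estimand and the sample size are untouched. The change is worth making because the threshold is meant to define clinically meaningful improvement and the e-Diary already holds the data.

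**What to change.** In SAP 7.2.5, for the ROC and the eCDF by anchor category only:

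1. Add an aligned analysis. Pair the Week 13 PGIC with the DYS change from the last menstruation that has at least 2 DYS diary days recorded by the PGIC date, scoring the days recorded by then. If there are fewer than 2, use the previous menstruation. The minimum is needed because each entry covers the last calendar day (Protocol 8.1.3), and about 7–11% of women in one simulation were visited on menses day 1 or 2.
2. Report this cut-off side by side with the one from the Week 12 score as now defined.
3. Tabulate by arm the share of scored menstruations that start after the visit, so that the size of the problem is known from the trial's own data.

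The primary endpoint stays as it is. The cost is SAP wording and one extra derivation from existing e-Diary data. The downside is that affected women's aligned score comes from an earlier menstruation, about 3–4 weeks before the PGIC, than the one in the primary endpoint. That is why both cut-offs should be shown.
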